Date: 07/08/2020

Protocol Version Number: 10

Principal Investigator: [name]

Project IRB #: 2008181

Application Title: Restoring vasodilator actions of insulin in patients with type 2 diabetes (Role of physical activity in restoring vascular insulin sensitivity in skeletal muscle of patients with type 2 diabetes).

Collaborating Investigators:

[name]

[name]

Statistical Analysis Plan

All statistical analyses were completed with SPSS Statistics (version 23) or GraphPad Prism software (version 8.1.1 or 9.3.0). Statistical comparisons were performed by two-tailed t test or analysis of variance (ANOVA), as appropriate, followed by Tukey's or Bonferroni adjusted pairwise comparisons when significant interactions were found. For all statistical tests, significance was accepted at $P<0.05$.

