Date: 07/08/2020

Protocol Version Number: 10

Principal Investigator: [name]

Project IRB #: 2008181

Application Title: Restoring vasodilator actions of insulin in patients with type 2 diabetes (Role of physical

activity in restoring vascular insulin sensitivity in skeletal muscle of patients with type 2 diabetes).

Collaborating Investigators:

[name] [name]

Study purpose: The purpose of the present project is to determine the effects of increased walking and shear stress on insulin-stimulated leg blood flow in sedentary patients with type 2 diabetes (T2D).

This study is classified as a clinical trial and is registered on Clinicaltrials.gov #NCT03203694.

Background: The notion that habitual aerobic exercise increases insulin-induced vasodilation is largely founded on rodent studies, hence the urgent need for human studies, especially in T2D. For example, it remains unknown if increased walking, the most common form of physical activity, enhances skeletal muscle vasodilator actions of insulin in T2D. In addition, the molecular mechanisms by which exercise improves vasoreactivity to insulin have not been examined in humans. We propose that in T2D patients who are sedentary (i.e., the vast majority), increased walking signifies a vital strategy to correct the impairment in insulin-stimulated leg blood flow. We hypothesize that this restoration of vascular actions of insulin is associated with a reduction of protein kinase C (PKC) activation and endothelin-1 (ET-1) expression in the vasculature of skeletal muscle. Indeed, we contend that increased physical activity and associated hemodynamic forces (e.g., shear stress) are a direct form of vascular medicine in humans. We capitalize on this concept by proposing that recapitulation of exercise-like hemodynamic signals (i.e., increased shear stress) using a non-exercise stimulus (i.e., lower body heating) will lead to favorable vascular adaptations, including enhanced vascular insulin sensitivity.

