Hypothesis A: Increased walking decreases vascular PKC activation and ET-1 expression, thus leading to an improvement in insulin-stimulated leg blood flow. To test this hypothesis, T2D subjects will be randomized to a control non-exercise group (n=20) or walking group (n=20). Subject randomization will be accomplished by computerized randomization software. The walking program will consist of 45 minutes of walking (at 60% of VO₂ peak) 5 days per week for 8 weeks. Exercise interventions of similar intensity and duration have produced beneficial vascular effects in humans. Three days per week of the exercise intervention will be supervised and conducted at the MU Physical Activity and Wellness (MUPAW) center, a core facility in our department. Subjects will have the option to perform the other two walking sessions per week on their own. Prior to initiating the walking program, subjects will undergo a standardized exercise stress test with assessment of ECG. The workload corresponding to 60% of heart rate reserve will then be identified. Our study physician, [name], oversees these tests and interprets the ECG following American College of Sports Medicine (ACSM) guidelines. These exercise interventions and protocols in patients with chronic disease are routine at MUPAW.

Prior to participating in the study, subjects will provide written informed consent, complete a medical health history questionnaire, and receive randomization into experimental groups (walking v. control). Subjects will then be provided with a FitBit pedometer to wear throughout the 8-week period to quantify steps taken. Subsequently, before and after the 8-week period, subjects will be scheduled to come to the University Hospital Clinical Research Center (CRC) for a single testing day (Experimental Visit). On the testing day, subjects will arrive at 7am after an overnight fast, having not taken medications, and not exercised for 24-48 hrs. The cohort of healthy control subjects (n=20) will participate in the experimental visit once, with no exercise intervention.

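### For the randomised walking v control comparison, ANCOVA on the pre-intervention value would generally be more precise than the t test or ANOVA the SAP names, at no data cost; the gain depends on a correlation and an SD ratio the documents do not give

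*SAP*

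**What the plan says.** The whole analysis plan is one short paragraph in the SAP. It states that "Statistical comparisons were performed by two-tailed t test or analysis of variance (ANOVA), as appropriate", followed by Tukey or "Bonferroni adjusted pairwise comparisons when significant interactions were found", with two-tailed significance at 0.05. No model, outcome summary or baseline covariate is named.

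The comparison at issue is in the protocol under Hypothesis A: "T2D subjects will be randomized to a control non-exercise group (n=20) or walking group (n=20". Allocation is by software: "Subject randomization will be accomplished by computerized randomization software". The same experimental visit is held twice: "before and after the 8-week period, subjects will be scheduled to come to the University Hospital Clinical Research Center". Every randomised participant who completes therefore has a pre-intervention value of each outcome, including the one in the study purpose, which is "to determine the effects of increased walking and shear stress on insulin-stimulated leg blood flow".

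The healthy cohort is different: "The cohort of healthy control subjects (n=20) will participate in the experimental visit once, with no exercise intervention".

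**The concern.** The reference to interactions most naturally points, for Hypothesis A, to a group-by-visit ANOVA of the two randomised arms. With two visits and one value per visit, that interaction test is the two-sample t test on change scores. It subtracts the baseline with a fixed slope of 1. ANCOVA estimates the slope instead, so it uses the baseline more efficiently in most settings.

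What is at stake is precision in a comparison of 20 v 20. The baseline means of the two arms will differ by chance, with a standard error of sqrt(2/20) = 0.32 SD. With equal pre and post SDs, a chance difference of that size moves the change-score estimate the other way by (1 - rho) x 0.316 SD: 0.19, 0.13 and 0.06 SD at rho 0.4, 0.6 and 0.8. ANCOVA removes this on average. That is where its gain comes from; it is not an additional benefit.

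**Working it through.** **Inputs.** From the documents: 20 per arm, one visit before and one after, two-sided 0.05. Not in the documents: rho, the within-arm post/pre SD ratio (k), a target effect and the planned power. I assume rho from 0 to 0.95, k from 0.8 to 1.3, 80% power, and the same rho and SDs in both arms. There is no stated power figure to reproduce.

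**Variances**, in units of the squared pre-intervention SD:
- Change score: 1 + k² - 2k·rho, with 38 df. At k = 1 this is 2(1 - rho).
- ANCOVA: k²(1 - rho²) x (1 + 1/36), with 37 df. The factor 37/36 is the cost of estimating the slope with 20 per arm.
- Follow-up-only t test: k², with 38 df.

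The detectable difference is a multiple of the standard error sqrt(2 x variance/20). From the noncentral t, the multiple is about 2.875 (38 df) or 2.877 (37 df).

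**Example, k = 1, rho 0.4.** Change score: variance 1.200, SE 0.346, detectable difference 0.996 SD. ANCOVA: 0.84 x 37/36 = 0.863, SE 0.294, detectable difference 0.845 SD. That is 15% smaller.

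**Equal SDs (k = 1):**

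| rho | Change score (SD) | ANCOVA (SD) | Reduction |
|---|---|---|---|
| 0 | 1.286 | 0.922 | 28% |
| 0.2 | 1.150 | 0.904 | 21% |
| 0.4 | 0.996 | 0.845 | 15% |
| 0.6 | 0.813 | 0.738 | 9% |
| 0.8 | 0.575 | 0.553 | 4% |
| 0.9 | 0.407 | 0.402 | 1% |
| 0.95 | 0.287 | 0.288 | none |

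Break-even is at rho about 0.94.

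**Unequal SDs.** Example, k = 1.15, rho 0.6: change score 1 + 1.3225 - 1.38 = 0.9425; ANCOVA 1.3225 x 0.64 x 37/36 = 0.870. The detectable difference goes from 0.883 to 0.849 pre-SD, a 4% gain. Repeating this over the range gives these reductions in detectable difference (a minus sign is a loss):

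| Post/pre SD ratio | rho 0.4 | rho 0.6 | rho 0.8 | Where ANCOVA is worse |
|---|---|---|---|---|
| 0.80 | 26% | 21% | 19% | nowhere (gain 19-37% over rho 0 to 0.95) |
| 1.00 | 15% | 9% | 4% | rho above about 0.94 |
| 1.15 | 10% | 4% | -1% | rho about 0.76 to 0.93 |
| 1.30 | 6% | 1% | -1% | rho about 0.64 to 0.86 |

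**Why the loss is bounded.** Without the slope penalty, the change-score variance exceeds the ANCOVA variance by (1 + k² - 2k·rho) - k²(1 - rho²) = (1 - k·rho)², which is never negative. ANCOVA can lose only the price of estimating the slope: sqrt(37/36) x 2.877/2.875 = 1.0145, or about 1.5% of the detectable difference at worst, reached when k·rho = 1.

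**Against a follow-up-only t test (k = 1).** That test detects 0.909 SD at any rho. ANCOVA is better above rho about 0.17. Below that it loses at most 0.922 - 0.909 = 0.013 SD.

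**Does the ANOVA already deliver this gain?** No. In a simulated 20 v 20 data set with two visits, the group-by-visit interaction F and the squared change-score t were identical (2.388).

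**The case against.** The strongest reply is that nothing here is wrong. Under randomisation, the t test and the change-score ANOVA are valid. With rho unknown, the gain could be anything from material to nil. That stands, and it is why this is an improvement and not a defect. But the unknown rho also favours ANCOVA, because the slope is estimated and need not be guessed, and the possible loss is far smaller than the possible gain.

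The comparator is also inferred. The SAP never says group by visit, and leg flow is read every 20 minutes over a 180-minute clamp, so the interaction could involve clamp time. The figures above hold for one value per visit. Which summary to use, and which outcome leads, is a separate gap that this point does not try to settle.

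The phrase about appropriateness might be stretched to include ANCOVA, but no covariate is named. If ANCOVA was meant, one sentence would say so.

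Three stronger readings are tempting and not supported:
- *The planned test is biased or has the wrong error rate.* It does not. Simulated type I error, at 20,000 trials per setting, was 4.6-5.2% for both methods.
- *The 15%, 9% and 4% gains, or the 0.94 break-even, apply generally.* They hold only with equal pre and post SDs, which the documents do not report.
- *The order of steps in Hypothesis A is itself a fault.* Participants "complete a medical health history questionnaire, and receive randomization into experimental groups (walking v. control" before the baseline visit. This means allocation could not be balanced on baseline flow. The baseline should be confirmed as taken before the intervention and unaffected by knowledge of the arm, but the change score needs the same assurance.

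**Conclusion.** The point holds as an efficiency improvement for the randomised comparison in Hypothesis A. ANCOVA is generally more precise than the change-score test. With equal SDs, the detectable difference falls by 15%, 9% and 4% at rho 0.4, 0.6 and 0.8. With a post SD 15-30% larger, the gain is about 6-10% at rho 0.4 and 1-4% at 0.6, with a loss of about 1% over part of the higher range. With a post SD 20% smaller, it is 19-37%. These figures rest on assumed values of rho and the SD ratio, similar variability in both arms, and one value per visit.

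A reader might infer that the trial is underpowered without ANCOVA. The documents state no target effect, SD or power, so that cannot be judged. Nor does the argument extend to the single-arm heating group or to the healthy controls, who are measured once and not randomised.

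**What to change.** In the SAP, add for Hypothesis A: the walking and control arms will be compared by ANCOVA, with the post-intervention value as the response and arm and the baseline value of the same outcome as terms, the baseline being measured before the walking or control period starts. Report the adjusted difference with its 95% CI.

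The cost is one sentence and one model term, with no new visits or measurements. Statistically it costs 1 degree of freedom and about 3% of variance (1/36) for the slope, so a loss of about 1% is possible in some settings. The SAP is written in the past tense. If outcome data have already been examined, the gain in precision remains, but the choice should be labelled as not prespecified.

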Inclusion and exclusion criteria: Men and women with T2D who are overweight and obese (BMI 25-50 kg/m2), 35-65 years of age, and sedentary (<60 minutes structured exercise/week) will be recruited from the local community and the University Hospital Cosmopolitan Diabetes Center. A cohort of non-obese (BMI 19-29kg/m2), recreationally active men and women aged 35-65 will be recruited to serve as healthy control subjects. Patients with T2D will be classified based on physician diagnosis. Exclusion criteria: 1) cardiovascular disease including myocardial infarction, heart failure, coronary artery disease, stroke; 2) renal or hepatic diseases; 3) active cancer; 4) autoimmune diseases; 5) immunosuppressant therapy; 6) excessive alcohol consumption (> 14 drinks/week for men; >7 drinks/week for women); 7) current tobacco use; 8) pregnancy; 9) foot ulcers; 10) diabetic neuropathy; 11) mobility limitations; 12) uncontrolled hypertension (≥180 systolic / 100 diastolic mmHg).

For the experimental studies utilizing an ingestible telemetry sensor to monitor the core temperature of subjects, the following exclusion criteria will also be applied: 13) swallowing or esophageal disorders, or impairment of the gag reflex for experimental studies using the telemetry sensor; 14) gastrointestinal tract diseases or disorders; 15) individuals scheduled for nuclear magnetic resonance (NMR)/magnetic resonance imaging (MRI) scanning while the telemetry sensor is in the body.

Sub-study: A separate cohort of men and women ages 18- 65 will be recruited from the local community. Same exclusion as that listed above will be applied.

Number of subjects to be enrolled and justification: We plan to enroll a total 120 subjects to test hypotheses A, B, and the sub-study described below. This number will allow for subject dropout and provide a sufficient sample size to establish the efficacy of the interventions.

Experimental Studies:

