On the Experimental Visit, body composition will be assessed with dual-energy X-ray absorptiometry. Subjects will then be placed supine in a guiet, climate-controlled room (22–23°C) and flow-mediated dilation in the brachial and popliteal arteries will be assessed as a marker of vascular function. A pressure sensor (tonomter, the size of a pencil) will be placed over the skin of the neck region to obtain the pressure wave form in the carotid artery. Next, the insulin clamp, coupled with measures of leg blood flow, will be performed following standard procedures at the University Hospital CRC. Subjects will be instrumented for measures of heart rate (using standard lead II ECG), arterial blood pressure (using automated sphygmomanometry and beat-to-beat via Finometer), and leg blood flow (using duplex Doppler ultrasound and contrast-enhanced ultrasound, CEU). After a minimum of 20 min supine rest, baseline cardiovascular measurements will be collected, blood samples obtained and the hyperinsulinemic-euglycemic clamp will start. Briefly, insulin diluted in 0.9% saline with 5 ml of the subject's blood is infused with a 10 min priming dose followed by a constant infusion at 40 mU·m-2·min-1, a dose used to mimic postprandial insulin concentrations. Glucose is maintained at fasting values throughout via a variable 20% dextrose infusion. Leg blood flow, arterial blood pressure, and heart rate will be collected for 5-min periods at 20-min intervals throughout the 180-min clamp allowing the magnitude as well as the temporal profile of these variables to be determined. For microvascular blood flow using CEU, measurements will be performed before and during the first 60 min of insulin stimulation. Briefly, assessment of microvascular perfusion utilizing CEU involves ultrasound imaging of the leg skeletal muscle and abdomen during the administration of one vial (1.3mL) of an ultrasound contrast agent diluted in 30mL of 0.9% saline that will be given using a handheld syringe pump through the IV at a rate of 2mL/min. This agent, called Definity, is composed of tiny microbubbles smaller than the size of a red blood cell. These bubbles stay inside the blood vessels and go where the red blood cells go. This contrast agent allows us to evaluate microvascular blood flow. Definity has been FDA approved for use in humans during ultrasound of the heart cavity and has been shown to be safe. The total volume of blood drawn per insulin clamp will be less than 120mL. During the hyperinsulinemic-euglycemic clamp, [name] will perform the skeletal muscle biopsies from the vastus lateralis muscle, following established procedures at the CRC. Skeletal muscle biopsies will be processed for molecular characterization via immunofluorescence, PCR, and Western blotting. Assessments will include expression/activity of PKC, MAPK, eNOS, and ET-1, among other targets related to insulin signaling and vascular health.

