pressure cuff inflation of 250mmHg.that is maintained for 5-minutes. A tonometer will be placed over the skin of the neck region to obtain the pressure wave form in the carotid artery. An intravenous catheter will be placed in an elbow crease for blood sampling and collection of endothelial cells. Endothelial cells will be collected using 2-4 sterile J-shaped guidewires that are sequentially advanced ~10 cm through the intravenous catheter and then retracted, and the cells recovered by washing the wires with a dissociation buffer. Subjects will be seated recumbently and given a 75g glucose beverage for the 2hr OGTT, during which, 5mL of blood will be sampled, blood pressure obtained (using an automatic blood pressure monitor), and leg blood flow (using duplex Doppler ultrasound) will be recorded every 15-minutes. At baseline, 10mL will be drawn. Accordingly, the total amount of blood drawn will be 50mL. The length of this visit will be 4-hours long.

The figure below (Figure 1.) provides a visual representation of the planned timeline of measurements. However, minor deviations from this timeline may occur dependent on subject and study personnel availability:

	Baseline	Heat Therapy (60mins/day)	Post-Intervention
		Day 1 Day 2 Day 3 Day 4 Day 5 Day 6 Day	ay 7 24h
Accelorometer	7d		
Pulse wave velocity measurements	↑	 	↑
Flow-mediated dilation tests	↑	 	↑
Femoral blood flow measurements	↑		↑
Oral glucose tolerance test	↑		↑
Endothelial cell biopsy	↑		1
Dual energy X-ray absorptiometry	↑	 	↑
Core temperature pill ingestion		↑ 1	

Figure 1. Planned timeline of measurements for Hypothesis B.

Sub-study:

Prior to participating in the study, each subject will provide written informed consent. Subjects will be scheduled to come to the University Hospital Clinical Research Center (CRC) for one testing day. On the testing day, subjects will arrive at 7am after an overnight fast, having not taken medications, and not exercised for 24-48 hrs. Upon arrival to the CRC, height, weight, and waist circumference will be measured.

Experimental Intervention:

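### The SAP names only t test or ANOVA for a leg-flow series of about 20 readings per randomised subject; if the time course is run as a classical repeated-measures ANOVA, incomplete subjects are dropped and an uncorrected group-by-time test rejects too often.

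*SAP*

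**What the plan says.** The SAP is a single paragraph. It states that "Statistical comparisons were performed by two-tailed t test or analysis of variance (ANOVA), as appropriate", followed by Tukey or Bonferroni "adjusted pairwise comparisons when significant interactions were found", with one two-sided 5% threshold for every test. It names no outcome, factors, within-subject model, sphericity correction, analysis population or missing-data rule.

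The protocol's Hypothesis A section describes the randomised comparison: "T2D subjects will be randomized to a control non-exercise group (n=20) or walking group (n=20"). Both groups attend an Experimental Visit before and after 8 weeks. At each visit a pre-insulin baseline is taken, and then "Leg blood flow, arterial blood pressure, and heart rate will be collected for 5-min periods at 20-min intervals throughout the 180-min clamp". The stated reason for this schedule is to capture both the size of the response and its course over time.

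In Hypothesis B, one unrandomised T2D group has an OGTT before and after heating, during which "leg blood flow (using duplex Doppler ultrasound) will be recorded every 15-minutes".

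On losses, the section on number of subjects says only that "This number will allow for subject dropout". It gives no rate.

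**The concern.** The data are a long, closely spaced series within each person, repeated at two visits. The stated methods are a t test and an ANOVA. Two features of the documents point towards a factorial repeated-measures ANOVA over the windows: the wish to see the time course, and the SAP's use of interactions as the gateway to pairwise comparisons.

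In its classical form that analysis has two weaknesses here.

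- It needs every cell filled, so one unusable window removes the subject. The randomised comparison then becomes one of subjects with complete data.
- Its F test over ordered windows assumes sphericity, which serially correlated flow readings are unlikely to meet. The group-by-time test is then too liberal. Because pairwise comparisons follow only a significant interaction, they would be opened too often as well.

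**Working it through.** **Readings per subject**
- Hypothesis A: 180/20 = 9 clamp windows, plus 1 baseline = 10 per visit. Two visits give 2 × 10 = 20.
- Hypothesis B: 120/15 = 8, plus 1 baseline = 9 per visit. Two visits give 2 × 9 = 18.

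**The plan's own figure.** No power, effect size, SD or dropout rate is stated, so there is no power calculation to reproduce. The one figure is the total of 120. It equals 20 + 20 (A, randomised) + 20 (A, healthy) + 20 (B, heating) + 20 (B, healthy) + 20 (sub-study) if the two healthy cohorts are separate, which leaves no places for dropout. If one healthy cohort serves both, the sum is 100 and 20 places (20/120 = 16.7%) are spare.

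**Lost windows, if all 20 readings must be present.** The loss rate p per window is assumed, with losses independent. The share of subjects incomplete is 1 − (1 − p)^20. For power I took the standardised effect that 20 per arm detects with 80% power in a two-sided 5% t test (d = 0.909). This is also an assumption.

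| p (assumed) | Incomplete | Complete per arm | Power |
|---|---|---|---|
| 0 | 0% | 20 | 80% |
| 0.5% | 9.5% | 18.1 | 76% |
| 1% | 18.2% | 16.4 | 71% |
| 2% | 33.2% | 13.4 | 62% |
| 5% | 64.2% | 7.2 | 36% |

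In a simulation of the post-minus-pre change (4,000 trials per setting), complete-case power was 70%, 62% and 33% at 1%, 2% and 5% loss. Averaging whatever windows were available kept all 40 subjects and gave 79% to 81%.

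**Missed second visit.** If 10% miss it (assumed), 20 × 0.9 = 18 per arm remain and power is about 75%. In the simulation, using available windows gave the same 75%.

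**Sphericity.** Null trials were simulated with 20 per arm and 10 windows at one visit, with no missing data and an assumed AR(1) correlation. The group-by-time F test at a nominal 5% rejected as follows.

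| AR(1) correlation | Uncorrected |
|---|---|
| 0.5 | 8.2% |
| 0.7 | 9.2% |
| 0.9 | 11.5% |

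With the Greenhouse-Geisser correction, the rate was 4.4% to 4.9% across the three settings. Repeat runs with other seeds agreed to within about one percentage point.

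**Which mixed model.** A model with a participant effect and AR(1) within visit, but no participant-by-visit effect, was also simulated under the null. When day-to-day visit variance was present, its arm-by-visit test rejected 10% to 16% of the time in one set of runs. It rejected 13.5% to 28% in another set, where that variance was 25% to 40% of the total. A t test on the change in per-visit means stayed at 4% to 6%. The participant-by-visit effect is therefore essential.

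**The case against.** The strongest reply is that the SAP says none of this. It does not put all windows into one ANOVA, delete incomplete subjects or leave P values uncorrected. A t test or ANOVA on a per-visit summary, such as mean clamp flow or change from baseline, fits the wording equally well and survives a lost window. That stands. A reader might infer that under this plan one unreadable window removes a randomised subject, or that the SAP commits the trial to a completers-only comparison. The documents do not support either reading, because both follow only if the windows are factors in a complete-case ANOVA.

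Other parts of the reply also stand:
- The loss rates and the 80% starting power are assumed. Independent losses are close to the worst case, since poor images probably cluster within a person and would then affect fewer subjects. The power column is for a t test on one value per subject, so it only approximates power in the ANOVA.
- The sphericity problem affects group-by-time tests over windows. With two visits, arm-by-visit has one degree of freedom and sphericity cannot fail there.
- A mixed model does not rescue a missed second visit. If leaving the walking programme depends on the unseen outcome, missing-at-random fails too.

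What the reply does not remove is the gap itself. A per-visit mean cannot show the time course that the protocol asks for, and the words *as appropriate* leave the choice between summary and series, and between corrected and uncorrected tests, open until after the data are seen.

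**Conclusion.** The concern holds in a conditional form. It is certain that t test and ANOVA are the only stated methods, that the schedule yields 20 readings per randomised subject (18 in single-arm Hypothesis B), and that neither document says how the series is modelled or how gaps are handled.

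If the time course is analysed by classical repeated-measures ANOVA, any missing window drops the subject, and an uncorrected group-by-time test has a type I error of about 8% to 12% under AR(1) correlation of 0.5 to 0.9. The inflation needs no missing data. The power loss is an illustration and not a prediction: 18% to 33% of subjects would be incomplete at an assumed 1% to 2% independent loss per window.

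The SAP should be changed, because a better method can be specified at low cost.

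**What to change.** **Hypothesis A.** Define the outcome as insulin-stimulated flow: the clamp readings as change from, or adjusted for, that visit's pre-insulin baseline, with one of the two chosen in advance. Treating the baseline as just another window would mix resting flow into the insulin response. Fit a linear mixed model to all available readings of all randomised T2D subjects in their assigned arm, with:
- fixed effects for arm, visit, time and their interactions;
- random effects for participant and for participant-by-visit;
- serial correlation within visit;
- small-sample degrees of freedom.

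The arm-by-visit contrast is the walking test.

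**Hypothesis B.** Use the same structure with visit and time only. There is no randomised arm, so arm terms have no meaning there.

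**Any repeated-measures ANOVA over windows that is kept.** Report the Greenhouse-Geisser corrected P value.

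**Missed second visits.** Keep these subjects in the analysis set, report the losses by arm, and add a sensitivity analysis to the missing-at-random assumption. State the expected dropout rate: at 10%, for example, 20 completers per arm need 20/0.9 = 22.2, so 23 randomised per arm.

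**Cost.** SAP wording and somewhat more analysis work, with no new data or procedures. A covariance structure must be named and missing-at-random assumed. If change from baseline is chosen, a lost baseline reading costs that visit's whole series, so the SAP should say how that case is handled. Little power is regained for subjects without a second visit.
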